- 29. Participation in any investigational drug trial within 1 month or 5 half-lives of the investigational drug, whichever is longest, prior to Screening.
- 30. Participants currently receiving (or unable to stop using prior to receiving the first dose of IMP) medications or herbal supplements known to be potent inhibitors of CYP3A (must stop at least 1 week prior), potent inducers of CYP3A (must stop at least 3 weeks prior), or drugs mainly metabolized by CYP3A with a narrow therapeutic index (must stop at least 1 day prior).
- 31. History of or current alcohol or substance abuse
 - Excessive alcohol use is defined as alcohol and/or substance abuse or dependence (as defined by the Diagnostic and Statistical Manual of Mental Disorders, 5th edition) in the past year or a history of alcohol or substance abuse, as determined by the Investigator.
- 32. Clinically significant abnormality on ECG, or an active infective process or any other clinically significant abnormality on Screening CXR taken within 4 weeks of the first dose, per Investigator opinion. If a CXR has been taken within the previous 3 months and results are available and normal, the CXR does not need to be carried out.
- 33. eGFR by the 4-variable Modification of Diet in Renal Disease equation of <45 mL/min/1.73 m² or any renal condition that would preclude the administration of gadolinium (e.g., acute renal insufficiency).
- 34. ALT, AST, amylase, or lipase $> 2 \times$ above ULN of laboratory reference range, total bilirubin $> 1.5 \times$ ULN, any other clinically significant laboratory abnormality.
- 35. B cell (CD19) count < 50% of the LLN at Screening.
- 36. Significant cytopenia, including neutrophil count < 1,500/mm³, platelet count < 75,000/mm³, absolute lymphocyte count < 800/mm³, or a white blood cell count < 3500/mm³

Note: for participants participating in the OLE Period after receiving Tecfidera during the 48-week main study, absolute lymphocyte count < 800/mm³ is considered an exclusion criterion.

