6.4.4.2 For Tecfidera Only

- For a lymphocyte count < 500/mm³ for > 24 weeks, Tecfidera should be temporarily withheld and the participant monitored until lymphocyte counts are back to the LLN. Once lymphocyte counts are back to LLN, the IMP can be restarted with additional follow-up monitoring of lymphocyte counts.
 - For an absolute lymphocyte count < 200/mm³ (Grade 4), Tecfidera should be permanently withdrawn and the lymphocyte count of the participant monitored.
- For a serious infection, after discussion with the Medical Monitor, consideration should be given to temporarily withholding Tecfidera until resolution of the infection.
- At the first sign or symptom suggestive of PML, Tecfidera should be withheld and an appropriate diagnostic evaluation conducted. MRI findings may be apparent before clinical signs or symptoms. Typical symptoms associated with PML are diverse, progress over days to weeks, and include progressive weakness on one side of the body or clumsiness of limbs. disturbance of vision, and changes in thinking, memory, and orientation leading to confusion and personality changes.
- Discontinue Tecfidera if clinically significant liver injury induced by Tecfidera is suspected.
- Patients should be instructed to discontinue Tecfidera and seek immediate medical care should they experience signs and symptoms of anaphylaxis or angioedema.
- For a flushing reaction (e.g., warmth, redness, itching, and/or burning sensation), Tecfidera should be temporarily withheld until symptoms have resolved. After the flushing reaction has resolved, Tecfidera should be restarted at a reduced dose (see Section 6.2).
 - Should a flushing reaction occur again, Teefidera should be permanently discontinued.

Grading Adverse Events for Investigational Medicinal 6.4.4.3 **Products**

For all laboratory abnormalities that correspond to CTCAE Grades 1 to 4, refer to the CTCAE, Version 4.03.

The reason for IMP withdrawal and the nature, duration, and results of any planned follow-up observations should be recorded in the appropriate section of the eCRF.

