17.3 Clinical Laboratory Evaluation

The clinical laboratory safety parameters measured in this trial and reported as part of the safety evaluation of hematology, biochemistry, and urinalysis, are specified in the protocol (Table 8 of the Clinical Trial Protocol, Section 7.4.3). The entire clinical laboratory section will be analyzed for OLE period. Some outputs not produced at time or Primary analysis and Blinded Extension analysis will also be repeated on the DBP for participants of the SAF analysis set.

Summaries of Clinical Laboratory Data

Laboratory values (including corresponding normal ranges) converted in standard units will be used for summary statistics, shift tables and boxplots. Gradable laboratory results will be classified according to the grades defined in NCI-CTCAE Version 4.03 as provided by the central laboratory. If a laboratory parameter has bi-directional toxicities (e.g., Potassium), both directions will be presented for the given parameter (i.e., Potassium Low and Potassium High). On-treatment values are defined as results of assessments made after the first IMP administration on Day 1. Laboratory results containing a modifier such as "<" or "\ge " will be handled case by case for summary statistics and will be reported both as collected in the database and as imputed in participant data listings. Data until the Safety Follow-up included will be used to derive the worst on-treatment values.

All parameters will also be presented according to the categories based on normal ranges: below normal limits (Low), within normal limits (Normal) and above normal limits (High).

Shift tables of baseline value (low, normal, high) versus worst on-treatment value, presented by treatment group, will be provided for hematology and biochemistry parameters.

Shift tables of baseline grade versus worst post-baseline grade, presented by treatment group, will be provided for hematology and biochemistry parameters.

Shift tables will be displayed using the OLE Baseline and worst on-treatment value or worst post-baseline grade during OLE period.

Directional laboratory tests (hematology, biochemistry) (Appendix 19.1) will be summarized by worst on-treatment value and by treatment group.

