- (ALT or AST) ≥ 3×ULN, (ALT or AST) ≥ 5×ULN, (ALT or AST) ≥ 10×ULN, (ALT or AST) ≥ 20×ULN
- TBILI ≥ 2×ULN
- Concurrent AST ≥ 3×ULN and TBILI ≥ 2×ULN
- Concurrent ALT \geq 3×ULN and TBILI \geq 2×ULN
- Concurrent (ALT or AST) $\geq 3 \times ULN$ and TBILI $\geq 2 \times ULN$
- Concurrent (ALT or AST) $\geq 3 \times ULN$ and TBILI $\geq 2 \times ULN$ and ALP $\geq 2 \times ULN$
- Concurrent (ALT or AST) $\geq 3 \times ULN$ and TBILI $\geq 2 \times ULN$ and ALP $\leq 2 \times ULN$ or missing

Concurrent measurements are those occurring on the same date.

Categories will be cumulative, i.e., a participant with an elevation of AST \geq 10×ULN will also appear in the categories \geq 5×ULN and \geq 3×ULN.

ALT values over time will be presented in a spaghetti plot for participants with on-treatment ALT grade 2 or higher elevation (i.e. grade \geq 2) during the OLE period, by treatment group. There will be 1 panel by treatment group. All plots by parameter will have the same scales to allow comparison between groups.

Kaplan-Meier estimates of proportion surviving event-free as a function of time will be presented for the following 4 types of events based on the ALT and eGFR parameters:

- Time from OLE first dose to first occurrence of ≥ grade 2 ALT (days) (for participants with OLE baseline grade < 2)
- Time from OLE first dose to first increase in ALT ≥ 1 grade above OLE baseline grade (days)

- Time from first Evobrutinib dose to first increase in ALT ≥ 2 grade above baseline grade (days) in DBP+OLE
- Time from first Evobrutinib dose to first increase in ALT ≥ 3 grade above baseline grade (days) in DBP+OLE.
- Time from OLE first dose to first occurrence of eGFR assessment equal to less than (<) 60 mL/min for participants with OLE baseline eGFR ≥ 60 mL/min by treatment group (days)

For the above figures based on OLE: time-to-event figures will be based on data from OLE weeks 0-end of treatment; a participant reaching end of treatment, without experiencing the event will have his/her event time right-censored at the time of the last ALT/eGFR assessment. A separate KM curve will be estimated for each of the 5 initial groups: Placebo + Evobrutinib 25 mg QD, Evobrutinib (any dose) and Tecfidera. For the figures based on DBP+OLE: the start time will be the first Evobrutinib dose irrespective of its occurrence during DBP or OLE phase.

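### The DBP+OLE curve for an ALT rise of 3 grades or more scores a rise from Grade 1 to Grade 3 as no event, so no time-to-event display over all evobrutinib exposure shows Grade 3 or higher ALT

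*SAP*

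**What the plan says.** The liver function part of SAP 17.3 lists four ALT time-to-event displays. Two cover all evobrutinib exposure, with the clock starting at the first evobrutinib dose in either phase: "Time from first Evobrutinib dose to first increase in ALT ≥ 2 grade above baseline grade (days) in DBP+OLE" and "Time from first Evobrutinib dose to first increase in ALT ≥ 3 grade above baseline grade (days) in DBP+OLE". Two cover the OLE only. One is an absolute level with a restricted risk set, "Time from OLE first dose to first occurrence of ≥ grade 2 ALT (days) (for participants with OLE baseline grade < 2"; the other is relative, "Time from OLE first dose to first increase in ALT ≥ 1 grade above OLE baseline grade (days".

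On grading, SAP 17.3 states: "Gradable laboratory results will be classified according to the grades defined in NCI-CTCAE Version 4.03 as provided by the central laboratory". Protocol 6.4.4.3 gives the range: "For all laboratory abnormalities that correspond to CTCAE Grades 1 to 4, refer to the CTCAE, Version 4.03". Protocol 5.3.2, criterion 34, excludes ALT only when it exceeds twice the upper limit of normal.

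Two further places bear on the meaning. The SAP's modification history (section 4) describes the plot added in version 2.0 as a first increase in ALT of at least 3, without mentioning a baseline grade. SAP 11.6 defines a study baseline and an OLE baseline. It assigns the OLE baseline to OLE tables and shows both in DBP+OLE listings, but it names neither for the DBP+OLE figures, whose bullets say only baseline grade.

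**The concern.** Two participants can reach the same ALT grade after the same exposure, and the 3-grade curve counts one and not the other because of where they started. The one not counted is the one whose ALT was already raised.

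Protocol 3.2 classes drug-induced liver injury as an important identified risk. In this SAP, the two relative-grade curves are the only liver displays that give time to onset over all evobrutinib exposure. A reader is likely to take the 3-grade curve as the cumulative incidence of Grade 3 or worse ALT, and as defined it is not that. SAP 17.3 also requires a group to have at least one event to appear in a time-to-event figure. If the curve is drawn by group, a group whose only Grade 3 rise came from a Grade 1 starter would be left out.

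**Working it through.** The plan states no figure for this point, so there is nothing to reproduce. The check enumerates the event rule.

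**Rule.** An event occurs when post-baseline grade ≥ baseline grade + k, with k = 2 or k = 3 (SAP 17.3). Grades run from 1 to 4 (Protocol 6.4.4.3), with 0 standing for no elevation.

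| Baseline grade | Needed, k = 2 | Worse grades scored as no event, k = 2 | Needed, k = 3 | Worse grades scored as no event, k = 3 | Needed, absolute Grade ≥ 3 |
|---|---|---|---|---|---|
| 0 | 0 + 2 = 2 | 1 | 0 + 3 = 3 | 1, 2 | 3 |
| 1 | 1 + 2 = 3 | 2 | 1 + 3 = 4 | 2, 3 | 3 |
| 2 | 2 + 2 = 4 | 3 | 2 + 3 = 5, not attainable | 3, 4 | 3 |

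For participants starting at 0, the 3-grade rule and an absolute Grade 3 rule are identical. They part at baseline Grade 1, where the 3-grade curve treats Grade 3 as no event. The 2-grade curve counts that rise.

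**Can Grade 1 starters be in the curve?** Criterion 34 admits ALT up to 2 × ULN. The documents do not print the CTCAE cut-offs for ALT. The only assumption needed is that Grade 1 begins below 2 × ULN.

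**Can Grade 2 starters?** Table 1 schedules no chemistry on Day 1, so the study baseline is normally the screening value to which criterion 34 applies. If Grade 2 begins above 2 × ULN (assumed), a Grade 2 study baseline is unlikely. It could arise if a later value serves as baseline for former placebo or Tecfidera participants.

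**Which baseline fits a clock that starts at first evobrutinib?**

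- Randomised to evobrutinib: the first study dose is the first evobrutinib dose, so the study baseline fits.
- Placebo: first evobrutinib comes after Week 24. The study baseline is about 24 weeks too early, and the OLE baseline falls after about 48 − 24 = 24 weeks of evobrutinib. Neither fits.
- Tecfidera: first evobrutinib is on OLE Day 1, so the OLE baseline fits. The study baseline is at least 48 + 4 = 52 weeks earlier (main study plus minimum washout).

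Neither defined baseline is the last pre-evobrutinib value for everyone.

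**What else covers the event?** Across DBP+OLE there is a by-participant listing of Grade 3 or higher biochemistry values and a summary of potential liver injury by R-value. The ULN-multiple counts, the spaghetti plot and the eDISH figures are specified for the OLE, and the grade shift tables use the OLE baseline and OLE values. None gives cumulative incidence or time to onset from first evobrutinib.

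**The case against.** The strongest reply is that the relative rule is deliberate and informative. The list sets absolute and relative events side by side, and a relative grade describes change from each participant's own starting level. That stands as a reason to keep the relative curves. It does not supply the missing absolute one.

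A second reply is that marked elevations are not hidden. The 2-grade curve, with the same start and exposure, counts a rise from Grade 1 to Grade 3, and the listings and summaries show the values. This also stands, and it confines the point to one curve.

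A reader might infer that both DBP+OLE curves lose large rises in participants with raised baseline ALT. The documents do not support that: for a Grade 1 starter the 2-grade curve loses only the rise to Grade 2. A reader might also infer that Grade 4 is practically out of reach, because Protocol 6.4.4.1 calls for permanent discontinuation at ALT of 5 × ULN or more. That goes too far. The same section allows case-by-case decisions after 24 weeks of exposure, and stopping drug does not cap an ALT value that is already rising.

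**Conclusion.** The point holds for the 3-grade curve. As worded, a Grade 1 starter has the event only at Grade 4, so the curve understates the cumulative incidence of Grade 3 or higher ALT, and no other DBP+OLE time-to-event display captures that level. This rests on the literal text and on Grade 1 ALT beginning below 2 × ULN.

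The size cannot be computed. It would need the share of participants at Grade 1 at baseline and their relative risk of a Grade 3 rise, and the documents give neither. Any percentage would only restate the values chosen for them.

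The intended event is itself uncertain. The modification history omits the reference to baseline grade, and the lead-in to the list announces 4 event types where five bullets follow, so the late addition may not have been fully edited. The unnamed baseline is a second gap in the same bullets. Both are worth correcting for an identified risk. Neither means that marked ALT elevation goes unreported.

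**What to change.** In SAP 17.3, either redefine the 3-grade curve as time from first evobrutinib dose to first ALT of Grade 3 or higher among participants below Grade 3 at baseline, or add that curve beside the two relative ones. Optionally do the same for Grade 2 or higher. This is the form of the SAP's own first OLE bullet. Align the modification history with whichever definition is meant.

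For all DBP+OLE ALT curves, name the baseline as the last non-missing value before the first evobrutinib dose. The data are scheduled: screening for those randomised to evobrutinib, Week 24 for placebo, and OLE Day 1 for Tecfidera.

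The cost is a few lines of text and one or two new or re-run figures. Participants already at or above the level at baseline leave the risk set and should be listed separately. On a given baseline, the Grade 3 result for participants with no elevation does not change.

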M2951 (25 mg tablets) will be administered orally daily for 48 weeks as needed based on the dose (e.g., 3×25 mg tablets for a 75 mg dose). Dosing will be either 25 mg once daily, 75 mg once daily, or 75 mg twice daily. Matched placebo tablets will be provided. For participants who choose to enroll in the OLE, M2951 may be administered for a total of up to 432 weeks.

Reference therapy: dose/mode of administration/dosing schedule: Tecfidera (120 or 240 mg hard capsules) will be used as an active control. For the first 7 days, Tecfidera is administered orally at 120 mg twice daily. Following this and for the duration of treatment, Tecfidera is administered orally at 240 mg twice daily orally. Detailed recommendations for the use of this product are described in the summary of product characteristics or prescribing information.

Planned trial and treatment duration per participant: Total duration of participation is approximately 440 to 448 weeks for participants who choose to participate in the optional OLE Period and approximately 392 days (56 weeks) for participants who do not participate in the optional OLE Period. Total duration includes:

- Screening: 28 days (4 weeks);
- Treatment: 168 days (24 weeks);
- Blinded treatment extension: 168 days (24 weeks);
- Tecfidera Washout for participants who were in Tecfidera arm: 4 to 8 weeks;
- Optional OLE Period (up to 384 weeks);
- 4-week Safety Follow-Up/End of Trial Visit: 28 days (4 weeks).

After completing the 48-week main study, participants will be offered the opportunity to participate in an optional OLE Period with M2951 up to 384 weeks.

Once the long-term follow-up study is open for enrollment in their country (i.e., once the Sponsor, upon agreement with Health Authorities/Ethics Committees, will have notified sites), participants in the OLE Period will have the option to transition into the long-term follow-up study under a new protocol for continued treatment. Upon Sponsor site notification, all participants will be asked to return for an OLE End of Treatment Visit within 30 days.

- For participants entering the long-term follow-up study under a new protocol, their OLE End of Treatment Visit in the current study is also their first visit in the long-term follow-up study. Therefore, these participants are neither required to enter the 4-week Safety Follow-up Period nor to undergo a 4-week Safety Follow-up Visit/End of Trial Visit.

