The purpose of this Integrated Analysis Plan (IAP) is to document technical and detailed specifications for the Final Analysis (FA) of data collected for protocol MS200527-0086 considering the early termination of the study; the primary endpoints of the phase 3 MS200527_0080 and MS200527_0082 studies were not met). The IAP is based upon Section 8 (Statistics) of the trial protocol dated 06 July 2023 (Version 8.0) and is prepared in compliance with International Conference on Harmonization E9.

This FA data report will include summaries of participant disposition, demographics, baseline characteristics, medical history, previous and concomitant medications, treatment exposure, efficacy evaluations, adverse events (AEs), deaths, selected laboratory parameters, vital signs, ECGs, and other endpoints related to safety monitoring up to the end of the study.

6 Objectives/Endpoints of the Final Analysis

The objective of the OLE Period of this study is to evaluate the long-term safety, efficacy, and HRQoL of M2951 for an additional 8 years, at an initial dose of 75 mg once daily which was eventually switched to 75 mg twice daily.

Endpoints for OLE Period:

- Efficacy and CCI endpoints at Week 48, 96, 144, 192, 240, 288, 336 and 384.
 - Number of gadolinium-enhancing T1 lesions;
 - ARR, based on protocol-defined qualified relapses;
 - Qualified relapse-free status;
 - Change from baseline in disability score based on EDSS score;

Safety as assessed by the nature, severity, and occurrence of AEs; vital signs; ECGs; absolute concentrations and change from Baseline in Ig levels;
 ; and clinical laboratory safety parameters.

For the Final Analysis, selected safety and efficacy endpoints based on data from OLE Day 1 to the end of the study will be evaluated.

For more details on the main study objectives please review section 4 Trial Objectives of the protocol.

7 Sample Size/Randomization

Sample size and randomization is described in the IAP for the primary analysis/blinded extension analysis performed after completion of the Double-Blind Period (DBP) of the study (Week 48/Week 52).

8 Overview of Planned Analyses

The protocol describes a total of 5 analyses that should be performed for this study. 4 of them have already been conducted according to the protocol. These are:

- Primary Analysis (when 100% of participants enrolled reached Week 24 of treatment, or prematurely discontinued from treatment)

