11.2 Presentation of Tables/Listings/Figures

TLFs will be presented using initial treatment groups (i.e., true treatment groups as "Placebo+Evobrutinib 25 mg QD", "Evobrutinib 25 mg QD", "Evobrutinib 75 mg QD", "Evobrutinib 75 mg BID", and "Tecfidera") and total population. A footnote will be added to indicate that participants switched from Placebo to Evobrutinib 25 mg QD for the second 24-week treatment period. A second footnote will be added to indicate that all participants switched to Evobrutinib 75 mg QD on OLE Week 0 and following protocol amendment V5 dated 21 November 2018, all participants still ongoing in OLE switched to Evobrutinib 75 mg BID.

All data recorded during the trial will be presented in individual data listings performed on the Safety OLE Analysis Set (SAF-OLE), unless otherwise specified. All listings will be sorted by treatment group, participant, and scheduled time point (where applicable), if not otherwise stated. Further details are provided in the appropriate section for the analysis of the specific parameter.

Tables and figures will be presented by treatment group and scheduled time point during OLE period (where applicable), unless otherwise specified. Tables and figures will be sorted by treatment group and chronological scheduled time point (where applicable).

Summary statistics as displayed in tables and figures will include data until end of study.

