To be included in a time-to-event figure, a group must have at least one event. Below the horizontal axis of the time-to-event figure, number of events and number of participants at risk will be displayed every 56 days (OLE period). The vertical axis may be restricted to 0.50 - 1.0, if none of the curves reach 50%.

eDISH (Evaluation of Drug-Induced Serious Hepatotoxicity) figures, as described in Merz *et al* (2014), will be presented for the OLE period. The figure produced will include 6 panels: 1 for each initial dose group and 1 pooled for all the participants who received Evobrutinib during DBP.

Listings containing Lab Test, Analysis Visit, Visit, Date of Measurement (Days under Treatment/ Days under OLE), Time Measurement, Result, Change from Baseline/OLE Baseline, Reference Range Low – High and NCI-CTCAE Grade for ALT, AST, Total Bilirubin and ALP for participants with a post-baseline LFT elevation will be provided for the OLE period.

Listings of Clinical Laboratory Data

By-participant listings of all individual hematology, biochemistry and urinalysis values present in the database will be provided. Only data during the OLE period (including OLE Baseline) will be displayed. A flag will indicate the first visit of switch from Evobrutinib 75 mg QD to Evobrutinib 75 mg BID during OLE period.

Laboratory values that are outside the normal range will be flagged in the data listings, along with corresponding normal ranges.

In this study, clinically significant lab abnormalities were recorded as adverse events. In lieu of a listing of clinically significant lab abnormalities for each domain, the following by-participant lab value listings will be provided:

- Listing of Grade ≥ 3 hematology values with data from DBP and OLE period
- Listing of Grade ≥ 3 biochemistry values with data from DBP and OLE period

• Listing of urinalysis values with Grade ≥ 3, value ≥ 2 times ULN (excluding values for Specific Gravity or pH parameters), or an increase of "++" for non-gradable parameters when applicable with data from DBP and OLE period

Additional analysis on the pancreatic and liver enzymes elevations will be performed.

The following outputs will be provided:

- 1. Kaplan-Meier figure for time to first occurrence of Lipase increased > 2 x ULN and Amylase increased > 2 x ULN separately for DBP and OLE.

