- 2. Abnormalities in lipase and amylase (i.e. higher the ULN). For the DBP information to be displayed by original treatment groups. For the OLE period only "Total" is needed.
- 3. Summary of potential DILI by R-Values and Periods for subjects with any ALT or AST elevation for DBP+OLE.

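### The double-blind lipase/amylase table has no stated split at the Week 24 switch, so its placebo-origin column can mix placebo and evobrutinib time

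*SAP*

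**What the plan says.** SAP 17.3 closes with three added outputs on pancreatic and liver enzymes. Item 1 is a Kaplan-Meier plot whose event is given as "time to first occurrence of Lipase increased > 2 x ULN and Amylase increased > 2 x ULN separately for DBP and OLE". Item 2 tabulates lipase and amylase abnormalities above ULN: "For the DBP information to be displayed by original treatment groups". For the OLE, item 2 asks for the total only.

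SAP section 7 describes the earlier analyses as "performed after completion of the Double-Blind Period (DBP) of the study (Week 48/Week 52"), so DBP in this SAP means the whole main study and not its first 24 weeks. The protocol synopsis gives the two parts as "Treatment: 168 days (24 weeks") and "Blinded treatment extension: 168 days (24 weeks"). SAP 11.2 labels the column Placebo+Evobrutinib 25 mg QD and adds a footnote that "participants switched from Placebo to Evobrutinib 25 mg QD for the second 24-week treatment period".

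Item 2 states no cut at the switch. Item 1 states no grouping, time origin or censoring rule. The five initial groups would apply to it only through the default in SAP 11.1.

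**The concern.** SAP 17.2.3 makes amylase and lipase elevation, including acute pancreatitis, an adverse event of special interest. Protocol 3.2 lists it as a potential risk for which no causal link is established. A placebo column is what helps a reader judge causality, and only Weeks 0 to 24 provide randomised placebo time.

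If item 2 is a cumulative count over the DBP, a participant whose first elevation appears after the switch is counted in the placebo-origin column. If evobrutinib raises these enzymes, that narrows the gap between arms, which is the less safe direction for a safety display. Nothing else in this SAP tabulates the topic with a placebo arm: the overview of events of special interest is for the OLE, and so are the routine laboratory summaries and shift tables.

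**Working it through.** The plan gives no lipase or amylase rate, so it has no figure of its own to reproduce here. The timeline can be reproduced; the risks below are assumptions.

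**1. Share of time.** 168 + 168 = 336 days (48 weeks). Placebo makes up 168/336 = 50% of planned treatment time in the placebo-origin column.

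**2. Share of measurements.** Protocol Table 1 schedules full chemistry at Weeks 4, 8, 12, 16, 20 and 24, then at Weeks 36 and 48. That is 6 visits before the switch and 2 after, so 25% of scheduled on-treatment measurements fall on evobrutinib. Counting the Week 52 follow-up, 6 of 9 fall before it. The LFT visits in Protocol Table 8 do not include amylase or lipase.

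**3. Dilution by time.** Let p0 and p1 be the 24-week risks on placebo and evobrutinib, with the switched arm carrying p1 after Week 24.

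- Placebo-origin column, 48 weeks: 1 − (1 − p0)(1 − p1)
- Evobrutinib column, 48 weeks: 1 − (1 − p1)²

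| p0 / p1 | Ratio at Week 24 | Placebo-origin, 48 wk | Evobrutinib, 48 wk | Ratio, 48 wk |
|---|---|---|---|---|
| 5% / 15% | 3.0 | 1 − 0.95×0.85 = 19.25% | 1 − 0.85² = 27.75% | 1.44 |
| 5% / 10% | 2.0 | 1 − 0.95×0.90 = 14.5% | 1 − 0.90² = 19.0% | 1.31 |
| 2% / 6% | 3.0 | 1 − 0.98×0.94 = 7.88% | 1 − 0.94² = 11.64% | 1.48 |

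In the first row, 48 weeks of uninterrupted placebo would give 1 − 0.95² = 9.75%, a ratio of 27.75/9.75 = 2.85. The longer window therefore explains only the step from 3.0 to 2.85. The mixing explains the step from 2.85 to 1.44.

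**4. Dilution by scheduled visits, 5% / 15%.** Spread each 24-week risk over 6 visits, then allow 2 more.

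- Placebo-origin: 1 − 0.95 × 0.85^(2/6) = 10.0%
- Evobrutinib: 1 − 0.85^(8/6) = 19.5%
- Ratio: 1.95, about 2.0

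**5. Wider range.** With a constant hazard, 24-week placebo risk of 2% to 15% and hazard ratio (HR) of 1.5 to 5, the risk ratio runs from 1.44 to 4.80 at Week 24 and from 1.16 to 1.60 over 48 weeks. For rare events the displayed rate ratio is 2HR/(1 + HR) by time, so 2 becomes 1.33 and 3 becomes 1.5. By visits it is HR/(0.75 + 0.25HR), so 2 becomes 1.6 and 3 becomes 2.0.

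**6. Dose.** All of this gives 25 mg QD the same effect as the comparison arm. If 25 mg QD had no effect, the first row would show 2.85. With a partial effect, the time-weighted ratio lies between 1.44 and 2.85.

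**The case against.** The strongest reply is that the trial has a clean placebo comparison elsewhere and that this table is neither hidden nor necessarily mixed.

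- **Week 24 primary analysis.** Protocol 8.3.2 makes laboratory safety part of a key secondary endpoint, with placebo limited to 24 weeks. Protocol 8.6 evaluates all Baseline-to-Week-24 endpoints at the primary analysis, and SAP section 8 says that analysis is done. This stands. A reader might infer that item 2 is the trial's only placebo contrast for pancreatic enzymes, but the documents do not support that. The earlier analysis plan is not supplied. SAP 17.3 says some DBP outputs are added because they were not produced then, which suggests this table is new but does not show that no other display existed.
- **Format of item 2.** It is unspecified. SAP Appendix 3 ends the DBP Week 24 biochemistry window at the first evobrutinib exposure of the second period, so a by-visit table would separate the two treatments. This stands, and it makes the concern conditional on a cumulative table.
- **Kaplan-Meier figure.** The original-group instruction belongs to item 2 only. If item 1 follows the default grouping, its curves up to Week 24 are uncontaminated, because later events cannot alter earlier estimates.
- **Labelling.** The column is named as a combination and footnoted, so it is not passed off as placebo. That discloses the mixture without letting a reader undo it.
- **Listings.** A listing of Grade 3 or higher biochemistry covers the DBP, and Protocol Table 7 puts Grade 3 for these enzymes at above 2 × ULN. It misses values between ULN and that threshold. By default listings use the OLE safety set, so participants who left before the OLE may be absent.
- **Other figures in the SAP.** A reader might infer that the infection and DBP+OLE ALT figures show the correct placebo handling. They do not: both start at first evobrutinib dose, drop placebo time, and answer an exposure question.

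**Conclusion.** The point holds for item 2. As written, the table can be produced with elevations first seen on evobrutinib counted in the placebo-origin column, and the reader then has no way to recover the placebo count. The direction of the distortion is toward no effect.

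Its size is not in the documents. Under assumed 24-week risks of 5% and 15%, a ratio of 3.0 falls to about 1.4 by time or about 2.0 by scheduled full chemistry visits. The figures rest on a cumulative table, a roughly constant risk over the period, and 25 mg QD acting like the comparison arm. The dilution would be smaller if 25 mg QD does less, and larger if risk concentrates soon after starting evobrutinib.

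For the Kaplan-Meier figure the gap is an unstated grouping and censoring rule, and it affects only the part after Week 24. SAP section 16 rules out hypothesis testing for efficacy, and these laboratory outputs are likewise descriptive, so no test or error rate is involved. This is a worthwhile, inexpensive improvement to one safety display and does not undermine the trial's placebo comparison as a whole.

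**What to change.** In SAP 17.3:

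1. **Item 2.** Show two panels. The first runs from Day 1 to the switch at Week 24, by original arm, with placebo follow-up ending at the first evobrutinib dose. The second runs from the switch to Week 48, with the former placebo arm labelled as newly exposed to evobrutinib 25 mg QD. State the denominator of each panel.
2. **Item 1, DBP figure.** State that curves are by initial treatment group, and censor the placebo arm at first evobrutinib dose.

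A further Kaplan-Meier from first evobrutinib dose over DBP and OLE is optional. It adds no placebo comparison.

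The cost is a few lines of SAP text and one extra table panel. The DBP biochemistry windows in SAP Appendix 3 already use the time of first evobrutinib exposure in the second period, so the cut can be programmed. The downside is fewer events per panel. With about 50 participants per arm, the assumed 5% and 15% correspond to 0.05 × 50 = 2.5 and 0.15 × 50 = 7.5 participants by Week 24, so counts should be printed beside the percentages. No visit, sample or clinical procedure changes.
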